10.2 Blood Cannabinoid Analysis

For participants who test positive for THC-COOH (50ng/mL cut-off) on the qualitative urine drug tests during screening and who also show inconclusive cessation results from quantitative urine analysis, an accredited and certified laboratory will conduct testing of blood cannabinoids (THC, 11-OH-THC, and THC-COOH) using high performance liquid chromatography-tandem mass spectrometry (LC-MS/MS).

10.3 Research Lab Biomarker Analysis

Biomarker laboratory analyses will be performed using plasma for CRP, IL-1 β , and IL-6 levels collected from all participants according to the Time and Events Table. For blood samples, a butterfly needle will be used to draw 30mL of blood into chilled EDTA vacutainer tubes. Samples will be immediately placed on wet ice. Plasma will be extracted by centrifugation in a refrigerated (4 °C) centrifuge at 1,300g for 10 minutes, aliquotted into individual tubes, and stored at -80 °C prior to shipment to the collaborating site at University of Colorado Boulder. Biomarker analyses will be performed by [name] in [name] laboratory at the University of Colorado Boulder in Boulder, Colorado (collaborating site). Concentrations of CRP, IL-1 β , and IL-6 will be quantified using commercially available enzyme immunoassay kits (R&D Systems, Minneapolis, MN, USA). These kits are highly specific and exclusively recognize CRP, IL-1 β , and IL-6 respectively, and not related peptides. Plasma samples are assayed in duplicate and measured using a microplate reader for 96-well format according to manufacturer's instructions.

11.0 Study Monitoring, Auditing and Documentation

Clinical Investigators and/or their site staff will be trained prior to the start of the protocol by the sponsor's clinical research staff. The clinical study site will be monitored by site visits and remote communication to the CI by representatives of the sponsor. The site will be monitored as appropriate for the rate of enrollment. During each monitoring visit, source data verification will be performed by a Clinical Research Associate (CRA) to ensure compliance, including accurate and complete recording of data on CRFs, source documents, and drug accountability records. CRFs supplied by the sponsor will be completed for each participant enrolled. Monitoring and auditing procedures of the

sponsor will be followed, in order to comply with Good Clinical Practice (GCP) guidelines and to ensure validity of the study data.

The sponsor will review the study documentation used for planning, conducting and monitoring of the study in order to ensure compliance with GCP and local regulations. This documentation includes, at minimum: the Investigator's Brochure, the Study Protocol, the CRFs and the ICF.

During or after the clinical protocol, the regulatory authorities, the IRB, and/or representatives of the sponsor may request access to all source documents, CRFs and other protocol documentation for on-site audit or inspection.

12.0 Data Analysis

Key Personnel, MAPS, and the biostatistician will agree on a detailed Statistical Analysis Plan prior to the beginning of recruitment. The biostatistician will perform an "intent to treat" (ITT) analysis using repeated measures analysis of covariance (ANCOVA) to compare demographics. Distribution of treatment dropouts will be examined by condition and if found to be unequal, the sponsor will control for group assignment in the ITT analysis.

Primary analysis of observer-blind CAPS-5 data collected at Baseline and end of Stage 1 will be conducted using ANCOVA with marijuana concentration as a between-subject factor and time of assessment as a within-group factor. If effects of marijuana concentration are detected at Stage 1, a similar secondary analysis will also be performed with Stage 2 data using Stage 1 data as a covariate for each outcome measure. Effect size will be estimated based on all outcome measures using Cohen's techniques. The biostatistician will conduct secondary exploratory analyses of weekly assessments of PCL-5, ISI, IDAS, IPF, WBR, CSSRS, MWC, CUDIT-R, DEQ and ACT scores using repeated measures ANCOVA or generalized linear mixed modeling, as described in the Statistical Analysis Plan. Statistical significance ($p < .05$) will be determined for all tests. All available data from repeated outcome assessments of all participants who are randomized, even if they withdraw from the allocated treatment prior to the primary endpoints, will be included in ITT analysis.

A repeated measures ANCOVA comparison of ratings on the DEQ and pulse will be conducted, with marijuana condition as the main factor in the analysis. If a main effect of marijuana concentration is observed then pairwise comparisons will be conducted to detect differences between each marijuana concentration.

Secondary exploratory analyses will be conducted examining weekly assessments of self-reported (via the ISI) and objective (via Actigraphy) measures of sleep. Independent repeated measures ANCOVAs will be conducted. In terms of self-reported sleep, weekly total scores from the ISI will be entered as the repeated measure with group entered as the IV. In terms of objective sleep (via Actigraphy) repeated measures ANCOVAs will be conducted with weekly total sleep time (TST), wake after sleep onset (WASO), sleep

onset latency (SOL), and sleep efficiency (SE) entered as the repeated measure in independent analyses and group entered as the IV. An ITT approach will be used. Statistical significance will be set at $p = .05$ for all analyses.

Quantitative levels of THC, CBD and their metabolites will be assessed in order to ascertain whether participants comply with only using the marijuana assigned to them during the study. If there is sufficient data, correlational analyses may also be conducted between biological cannabinoid levels and clinical outcomes to determine whether there is a dose-response effect between cannabinoid exposure and clinical response.

Prognostic value of CRP, IL-1 β and Il-6 will be examined using two regression analyses, one between biomarker values gathered at Baseline and at the primary endpoint CAPS-5 global severity score, and another between biomarker values collected after two weeks of cessation and the CAPS-5 global severity score at the end of Stage 1.

Qualitative safety analyses will examine Daily Diaries with summary tables listing maximum severity and duration, concomitant medications/therapies, and AEs with frequencies and percentages tabulated overall and by concentration group. Spontaneously reported reactions will be separated from unexpected AEs during analysis and presented separately in summary tables. Statistical analyses will be conducted to evaluate safety and AEs by marijuana treatment condition and individual demographic characteristics (e.g. gender, history of cannabis use, concomitant medication/drug use, baseline CAPS-5 score).

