3.1 Primary Objective

To compare independent effects of three active concentrations of smoked marijuana and placebo on PTSD symptom severity measured by changes in CAPS-5 total scores during 3-weeks of *ad-libitum* self-administration during Stage 1 of the study protocol.

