5.0 Methods

5.1 Assessments and Measures

5.1.1 Outcome Measures

Primary Outcome Measure:

The Clinician-Administered PTSD Scale (CAPS-5) [78] is a semi-structured clinical interview administered by a blinded IR and is used to assess index history of DSM-5-defined traumatic event exposure [79], including the most distressing event, time since exposure, and total number of exposures, as well as frequency and severity of posttraumatic stress symptoms, as evidenced by CAPS-5 total score. The CAPS-5 provides diagnostic status (presence versus absence) of PTSD as well as PTSD symptom severity. Changes in the CAPS-5 total score will be used as the primary PTSD outcome measure, and will be the primary determinant of effect size for this pilot study. The IR will administer the CAPS at visits described in the Time and Events table either in person or via telemedicine. IRs will receive training on administering this measure from a research reliable trainer. Interviews will be recorded in as many instances as necessary to establish reliability of a random selection of interviews for accuracy. The CAPS-5 will be

administered by trained interviewers throughout the study, who will be supervised by qualified personnel.

Secondary Outcome Measures:

The PTSD Checklist (PCL-5) with LEC plus criterion A (at baseline only) [80] is a 20-item self-report questionnaire in which respondents indicate the presence and severity of PTSD symptoms, derived from the DSM-five symptoms of PTSD [79]. Participants indicate how much distress they have experienced due to symptoms such as “Repeated, disturbing memories, thoughts, or images of a stressful experience from the past,” “Trouble remembering important parts of a stressful experience from the past,” and “Feeling irritable or having angry outbursts” on a five-point Likert-type scale (1=*not at all*, 5=*extremely*). The total PCL-5 score (a sum of all 20 items) provides an index of overall PTSD symptom severity.

The Inventory of Depression and Anxiety (IDAS) [81] is a 64-item self-report measure of depression and anxiety symptoms. Factor analytic research indicates that the IDAS has strong convergent and discriminate validity, as well as criterion validity [82]. Additionally, factor analytic research indicates that the general depression and anxiety subscales of the IDAS differentiate anxiety from depression [81, 82].

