12.1 Statistical Power

The proposed study is a pilot investigation intended to gather preliminary data on the safety and efficacy of marijuana in people with chronic, treatment-resistant PTSD. Because of their exploratory nature, pilot studies are often not powered for detecting the desired effect. Because it is a pilot study in a small sample, results will be used to assess variability of the outcome measures as inputs for calculation of sample sizes for adequately powered subsequent studies. This study will be the first to examine the effects of marijuana on PTSD.

This pilot RCT is the first study of its kind intended to gather estimates of effect size of marijuana for PTSD. In the absence of published effect sizes of marijuana for PTSD, possible effect sizes are estimated to be 0.4 (small to medium effect) for a between-subject comparison to ensure an adequately powered study size, based on a recent meta-analysis conducted with the National Center for PTSD [172]. Thus in the proposed study, $N=76$ with 19 participants randomized to each group will have 82% power to detect these or greater differences between groups on the same primary outcome measure (change in CAPS-5 total score) used to obtain FDA approval for PTSD medications. Similar calculations would apply for secondary analyses.

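### The primary CAPS-5 analysis names no baseline covariate and so gives up precision, and its rule for unequal dropout does nothing in that model

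*Protocol*

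**What the plan says.** The primary outcome is a change. Protocol section 3.1 refers to "PTSD symptom severity measured by changes in CAPS-5 total scores", and section 5.1.1 states: "Changes in the CAPS-5 total score will be used as the primary PTSD outcome measure".

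Section 12.0 takes CAPS-5 at Baseline and at the end of Stage 1 and analyses it by "ANCOVA with marijuana concentration as a between-subject factor and time of assessment as a within-group factor". It does not say what the covariate is or which term of the model is the primary test. The next sentence makes a Stage 2 analysis conditional ("If effects of marijuana concentration are detected at Stage 1") and does name a covariate for it: "a similar secondary analysis will also be performed with Stage 2 data using Stage 1 data as a covariate for each outcome measure".

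On dropout, section 12.0 says that its distribution will be examined by condition and, "if found to be unequal, the sponsor will control for group assignment in the ITT analysis". It also keeps in the ITT analysis "All available data from repeated outcome assessments of all participants who are randomized".

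Section 12.1 claims, for 76 participants at 19 per group and an effect size of 0.4, "82% power to detect these or greater differences between groups on the same primary outcome measure (change in CAPS-5 total score". Section 4.2 stratifies randomization by site (two sites) and allows about 116 randomized for 76 Stage 1 completers.

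**The concern.** An analysis labelled ANCOVA normally has a covariate. Here the obvious one, baseline CAPS-5, sits on the response side, so the later, secondary analysis is adjusted for the earlier score while the primary analysis, as written, is not. Baseline CAPS-5 and site are recorded for everyone randomized. Using them as covariates costs almost nothing and can only modestly hurt, while the possible gain is worthwhile with 19 per arm.

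The dropout sentence is a different kind of problem. It reads as a remedy for unequal dropout, but concentration group is already what the primary model tests. A reader could believe that unequal dropout has been provided for when, for the primary comparison, it has not. The allowance for non-completion is large, and CAPS-5 is taken at Screen 2 (section 5.2.3) and next at Visit 5 (section 5.2.9). A participant who leaves in between and is not evaluated has no post-baseline CAPS-5.

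**Working it through.** **1. The plan's own figure.** Inputs from section 12.1: 4 groups, N = 76, effect 0.4. Section 12.0 gives alpha 0.05. Reading 0.4 as Cohen's f and using the omnibus F test on 3 and 72 df:

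noncentrality = N × f² = 76 × 0.16 = 12.16, so power = 82.3%.

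This reproduces the stated 82%.

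**2. What the written model tests.** With two time points, the concentration-by-time F is the same as the one-way F on change scores. In a simulated data set both came to 2.919. Since the outcome is change, this is the relevant term, and it is a valid test under randomization.

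**3. Gain from adjustment.** Let ρ be the baseline-endpoint correlation and r the baseline SD divided by the endpoint SD. Neither is in the protocol. I assume ρ = 0.2, 0.5, 0.8 and r from 0.7 to 1.0. A ratio below 1 is plausible because section 4.3.1 requires a baseline CAPS-5 of at least 25, which narrows the baseline spread.

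var(change) / residual var(ANCOVA) = (r² + 1 − 2ρr) / (1 − ρ²) = 1 + (r − ρ)² / (1 − ρ²), which is never below 1.

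The ANCOVA f² is 0.16 times this ratio. Example with r = 1 and ρ = 0.5: 1 + 0.25/0.75 = 1.333; noncentrality = 12.16 × 1.333 = 16.2; power with 2 df spent on baseline and site (70 residual df) = 92.3%.

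Power of the adjusted test, with the difference from 82.3% in points:

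| r | ρ = 0.2 | ρ = 0.5 | ρ = 0.8 |
|---|---|---|---|
| 1.0 | 96.9% (+14.6) | 92.3% (+10.0) | 86.4% (+4.1) |
| 0.8 | 93.1% (+10.8) | 86.7% (+4.4) | 82.3% (about 0) |
| 0.7 | 90.7% (+8.4) | 84.4% (+2.1) | 83.4% (+1.1) |

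**4. Worst case.** When r = ρ the variance ratio is 1, and adjustment only costs. The formula charges just the 2 df (82.34% to 82.28%) and ignores the variance from estimating the baseline slope. Simulation with baseline and site in the model (40,000 replicates, r = ρ = 0.2, 0.5, 0.7, 0.8) includes it: change test 82.5, 82.5, 82.3, 82.4%; adjusted test 81.7, 81.7, 81.7, 81.8%. The loss is about 0.6 to 0.9 points. The tabulated gains are optimistic by up to about the same amount.

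**5. The dropout rule.** In a simulated data set, the group indicators were entered a second time in a model that already contained them. The design rank stayed at 5, the residual sum of squares stayed at 80.2406, and fitted values agreed to rounding error (4 × 10⁻¹⁶). No estimate or test changes.

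**6. How often the rule might be called on.** Planned non-completion: 1 − 76/116 = 40/116 = 34.5%.

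**The case against.** The strongest reply on the model is that nothing is invalid: the endpoint is change, the written analysis tests change, and the power statement agrees with it. That stands. A reader might infer that the primary test is biased or misses its stated power; the protocol does not support this. A reader might also infer that the group main effect, diluted by baseline, is what will be tested. The term is not named, but sections 3.1, 5.1.1 and 12.1 all define the outcome as change, which points to concentration-by-time.

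A second reply is that section 12.0 defers detail to an SAP, which is not at hand. It would go too far to say that an adjusting SAP must contradict the protocol: a repeated-measures model with baseline in the response and a common baseline mean across arms fits the text and recovers essentially the same precision. What stands is that the protocol names a covariate for Stage 2 and none for the primary analysis, and does not say that baseline means are constrained.

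Third, the gain depends on two unknowns and may be small. That is correct. Nor is 76 a ceiling on the analysed number: all available data are kept, and section 5.3 seeks outcome evaluations after withdrawal where possible. At f = 0.4 the change test has 89% power at N = 90 and 96% at N = 116.

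On dropout, it would be too broad to call the rule empty everywhere. The sentence follows one about comparing demographics, so its target is unclear. Some planned analyses, such as the biomarker regressions, are described without a group term, and adding one there could change results. The rule is empty where group is already in the model, as in the primary CAPS-5 analysis. Retaining available data, evaluating after withdrawal and enrolling to 76 completers limit missing data or hold the completer count; they do not adjust the comparison when dropout differs by arm.

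**Conclusion.** The point holds as a cheap improvement to the primary model and as a wording error in the dropout rule for that model. The planned concentration-by-time test is valid and matches its 82% power, but it leaves baseline information unused. The benefit ranges from about 0 to 15 power points under the assumed correlations and SD ratios, and is about 0 to 4 points in the less favourable part of that range (ratios of 0.7 to 0.8, correlations of 0.5 to 0.8). If the ratio happens to equal the correlation, the cost is under 1 point. These figures rest on reading 0.4 as Cohen's f on the change scale with 76 analysed.

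Controlling for group assignment cannot correct unequal dropout in a model whose tested factor is group. A reader might infer from this that the trial's result will be biased by some amount in some direction. The protocol gives no basis for that, and no size or direction of dropout bias is claimed.

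**What to change.** In section 12.0, define the primary test as the concentration term of an ANCOVA of end-of-Stage-1 CAPS-5 with baseline CAPS-5 and site (the randomization stratum) as covariates, or of an equivalent repeated-measures model with a common baseline mean. State that this same term decides whether the Stage 2 analysis is triggered.

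Delete the rule on controlling for group assignment as far as it concerns the primary CAPS-5 model. Put in its place a missing-data approach that uses data already collected, for example imputation from baseline CAPS-5 and the weekly PCL-5 (section 5.2.8), with a sensitivity analysis. An endpoint-only ANCOVA would otherwise omit participants who have only a baseline score. The details can go in the SAP.

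Cost: rewording one section, some analysis work, two degrees of freedom, and under 1 point of power in the worst case. No new visits, assessments or participants are needed.

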3.2 Secondary Objectives

The following secondary objectives will be used to support the results of the primary objective:

1. Assess independent effects of three active concentrations of marijuana and placebo in reducing self-reported symptoms of PTSD with the PCL-5, anxiety and depression with the IDAS, and improving psychosocial functioning with the IPF and WBR (self-report and observer) among veterans during Stage 1.
2. Assess independent effects of three active concentrations of marijuana and placebo in reducing self-reported symptoms of PTSD with PCL-5, anxiety and depression with IDAS, and improving psychosocial functioning with the IPF and WBR (self-report and observer) among veterans during Stage 2.
3. Assess comparative efficacy between placebo and each active dose of marijuana based on a within-subjects analysis of PTSD symptoms as measured by the CAPS-5 in crossover participants at Baseline, End of Stage 1, Stage 2 Baseline, and End of Stage 2.
4. Assess whether Stage 2 crossover participants' preferences for marijuana concentrations in Stage 1 and Stage 2 correlate with reduction in PTSD symptoms as measured by the CAPS-5 total score.
5. Assess whether participants experience a clinically significant increase in PTSD symptoms based on CAPS-5 and PCL-5 total scores during the washout period between Stage 1 and Stage 2 compared with measures assessed at Baseline and during Stage 1.
6. Explore correlation of treatment outcomes measured by CAPS-5 score with objective changes in sleep via Actigraphy throughout the study and self-reported

- changes in sleep quality using the ISI on a weekly basis.
7. Explore correlation of Daily Diary items related to sleep with objective changes in sleep via Actigraphy and self-reported changes in sleep quality using the ISI on a weekly basis.
 8. Explore correlation of treatment effects measured by CAPS-5 total score with amount of marijuana used based on Daily Diary across Stage 1 and Stage 2.
 9. Explore treatment outcomes measured by CAPS-5 total score by marijuana concentration, with concomitant substance and medication use as a covariate throughout the treatment period.
 10. Explore durability of treatment outcomes measured by CAPS-5 total score, with any PTSD treatments based on the LTFU questionnaire treated as a covariate, six months after completing Stage 2.

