4.0 Protocol Design

This Phase 2 randomized, placebo-controlled, triple-blind, crossover, multi-site study will assess the safety and efficacy of four types of smoked marijuana to manage chronic, treatment-resistant PTSD symptoms among 76 veterans in an outpatient setting. The study will consist of a baseline period and three distinct study stages, which are described in detail below.

An initial 2-week screening period will be conducted to determine study eligibility prior to randomization, to obtain baseline measures of PTSD and substance use, to conduct study training, and ensure participants are willing and able to attend scheduled appointments and complete the study procedures.

Following randomization, participants will complete Stage 1, a three-week period of *ad-libitum* marijuana self-administration followed by a two-week period of marijuana abstinence (Cessation 1). This will be immediately followed by Stage 2, another three-week period of marijuana self-administration and two-week period of abstinence (Cessation 2). Stage 1 and Stage 2 will consist of identical procedures and measures, but the marijuana available to individual participants will vary.

During Stage 1, participants will be randomized to receive High THC, High CBD, THC/CBD, or Placebo marijuana to self-administer (up to 1.8 g/day) for the 3-week marijuana use period. As described in Section 4.2, randomization will be balanced across drug conditions (N=19 per marijuana type; total N=76). During Stage 2, the Placebo marijuana condition will be removed and all participants will be re-randomized to receive a different type of marijuana than they were assigned in Stage 1. Thus, Stage 2 will permit a within-subjects comparison of changes in CAPS-5 total score as a function of marijuana concentration, including differences in preferences for a specific marijuana concentration by self-report, and the removal of placebo as a possibility ensures that all study participants receive active marijuana at some point during the study.

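### The Stage 2 concentration analysis depends on an undefined Stage 1 detection, although Secondary Objectives 2 and 3 and the purpose of Stage 2 carry no such condition

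*Protocol*

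**What the plan says.** Protocol Section 12.0 first sets out the primary Stage 1 analysis: an ANCOVA of CAPS-5 with concentration between subjects and time within subjects. It then says: "If effects of marijuana concentration are detected at Stage 1, a similar secondary analysis will also be performed with Stage 2 data". Stage 1 data serve as the covariate, for each outcome measure.

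The objectives and the design section set no such condition:

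- Section 3.2, Objective 2, covers PCL-5, IDAS and function in Stage 2: "and improving psychosocial functioning with the IPF and WBR (self-report and observer) among veterans during Stage 2".
- Section 3.2, Objective 3, covers the crossover: "Assess comparative efficacy between placebo and each active dose of marijuana based on a within-subjects analysis of PTSD symptoms". The measure is CAPS-5 at Baseline, End of Stage 1, Stage 2 Baseline and End of Stage 2.
- Section 4.0 gives the purpose of the second stage: "Stage 2 will permit a within-subjects comparison of changes in CAPS-5 total score as a function of marijuana concentration".

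Section 12.1 supplies the planning figures: "possible effect sizes are estimated to be 0.4 (small to medium effect) for a between-subject comparison", and "with 19 participants randomized to each group will have 82% power to detect these or greater differences between groups". Section 12.0 sets the 0.05 level for all tests.

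**The concern.** The protocol says two things. The objectives and design promise a Stage 2 comparison, while the analysis section makes it depend on the Stage 1 result. Section 12 describes no other Stage 2 or crossover comparison of CAPS-5 by concentration, so for the main outcome the conditional sentence is the only stated route.

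The condition saves nothing. Section 4.0 re-randomises all participants into Stage 2, and Section 4.2 keeps the blind until everyone has finished and the database is locked. The exposure, cessation periods and CAPS-5 interviews will already have taken place when the rule is applied.

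The trigger is also open. Section 12.0 does not say whether an effect is detected by the omnibus test or by a pairwise test. Nor does it say whether the gate works through CAPS-5 alone or separately for each outcome. Whether Stage 2 is compared could therefore be settled after the Stage 1 result is known.

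Section 12.1 describes a pilot meant to inform the size of later trials. Stage 2 estimates serve that aim whichever side of 0.05 Stage 1 falls.

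**Working it through.** The chance that the gate stays shut is 1 minus the power of the Stage 1 test.

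**Inputs from the protocol.** Four groups of 19, N = 76, effect size 0.4 with no metric named, stated power 82% (Section 12.1); level 0.05 (Section 12.0); about 116 randomised (Section 4.2).

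**Assumptions.** Detection means a significant four-group F test, unless stated otherwise. The correlation between baseline and endpoint CAPS-5 is not given; I take r from 0 to 0.7.

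**Formula.** Noncentral F with 3 and N − 4 degrees of freedom (one fewer in the denominator with a baseline covariate). The noncentrality is λ = N·f² / (1 − r²), where f² is the mean squared deviation of the group means in SD units.

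**Step 1: reproduce the 82%.** With 0.4 as Cohen's f and r = 0, λ = 76 × 0.16 = 12.16 and power is 82.3%. A group-by-time test with f = 0.2, two time points and correlation 0.5 has the same noncentrality, 76 × 2 × 0.04 / 0.5 = 12.16, and the same power. On this reading the analysis is skipped in about 18% of trials.

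**Step 2: read 0.4 as a standardised mean difference d.** A two-arm comparison of 19 v 19 then has 22.4% power (two-sided t), so this reading does not give 82%. For the omnibus test with N = 76 and r = 0:

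| Pattern of means (SD) | f² | λ | Power | Skipped |
|---|---|---|---|---|
| Two arms 0.4, two 0 | 0.0400 | 3.04 | 26.5% | 73.5% |
| All three actives 0.4, or one arm 0.4 | 0.0300 | 2.28 | 20.5% | 79.5% |
| Evenly spaced 0 to 0.4 | 0.0222 | 1.69 | 16.1% | 83.9% |
| Extremes 0.4 apart, others midway | 0.0200 | 1.52 | 14.8% | 85.2% |

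The label small to medium fits this reading better: f = 0.4 would mean a largest difference between groups of about 0.8 to 1.1 SD for these patterns.

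**Step 3: vary the assumptions.**

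| Setting | Skipped |
|---|---|
| d = 0.4, N = 76, r = 0.5 | 65-81% |
| d = 0.4, N = 76, r = 0.7 | 51-74% |
| d = 0.4, all 116 analysed, r = 0 | 60-79% |
| d = 0.4, all 116 analysed, r = 0.7 | 30-61% |
| f = 0.4, all 116 analysed, r = 0 | about 4% (power 95.8%) |
| d = 0.4, N = 76, any one of three unadjusted pairwise tests v placebo counts (simulated) | 57% (all three actives differ) or 72% (one differs) |
| No true effect, omnibus test | 95% |

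The rows with 116 are a favourable limit, because Section 4.2 sets 116 to allow for dropout and stops enrolment once 76 have completed Stage 1.

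**The case against.** The strongest reply has four parts.

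1. *The protocol's own figure gives a modest risk.* The 82% is reproduced with 0.4 as Cohen's f, and the gate then opens about four times in five. This stands. A reader might infer from the d = 0.4 figures that Stage 2 will most likely go unanalysed. The document does not establish that, because it never names the metric.

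2. *Much of Stage 2 is outside the gate.* Section 12.0 plans exploratory analyses of PCL-5, ISI, IDAS, IPF, WBR and other measures without condition or stage limit, and these include every measure in Objective 2. Its safety and adverse event analyses are ungated too. This also stands. A reader might infer that half of the design is lost, or that Objectives 2 and 3 both go unanswered; neither follows. Section 12.0 also promises effect sizes for all outcome measures without condition, so it is not shown that the pilot loses its estimates.

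3. *The gated sentence repeats the Stage 1 ANCOVA on Stage 2 data and does not name the within-subject analysis of Objective 3.* That is correct, and an SAP may specify that analysis. Hence Objective 3 is at risk rather than expressly dropped. But Section 12 offers no other CAPS-5 comparison for it, and an SAP would not remove the conflict within the protocol.

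4. *Gatekeeping is legitimate.* It is, for deciding which p-values support a claim. It is no reason to leave a planned secondary analysis unrun.

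A reader might also suspect that Stage 2 estimates reported only after a positive Stage 1 are biased by selection. Stage 2 is a fresh randomisation with Stage 1 data as covariate, and the size of any such bias has not been worked out, so I do not rely on it.

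**Conclusion.** The conflict is real and certain as a matter of wording: Section 12.0 conditions the only Stage 2 CAPS-5 comparison by concentration that it describes on an undefined Stage 1 finding, and Sections 3.2 and 4.0 do not.

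The size of the consequence depends on what 0.4 means. At 19 per arm with no gain from baseline, the analysis is skipped in about 18% of trials if 0.4 is f and in about 73-85% if it is d. Baseline correlation, a larger analysed sample or a looser definition of detection lowers these figures. With no true effect the omnibus gate stays shut in 95%. The practical loss is mainly the Stage 2 CAPS-5 comparison and, with it, a secure answer to Objective 3. The protocol should be changed on this point, but the Stage 1 primary analysis is not affected.

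**What to change.** In Section 12.0, delete the opening condition of the sentence on Stage 2. State that the Stage 2 concentration analysis and the within-subject CAPS-5 analysis of Objective 3 are always run, and are reported as secondary with estimates and confidence intervals.

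If the sponsor wants a gate, define detection (which test, which outcome, what level) and apply it only to whether a Stage 2 p-value may be called confirmatory.

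The cost is a sentence or two of text. No new data, visits or participants are needed.
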